| 14.2. COVID-19 SYMPTOM DIARY SCORING | 37 |
| 14.3. GLOBAL IMPRESSIONS QUESTIONS | 37 |
| 14.4. EQ-5D-5L | 38 |
| 14.5. IMPUTATION RULES | 38 |

List of Abbreviations

| | |
|------------|-----------------------------------------------------------------------------------------------------|
| 3CLpro | SARS-CoV-2 3-chymotrypsin–like cysteine protease |
| AE | adverse event |
| ANCOVA | analysis of covariance |
| ATC | Anatomical Therapeutic Chemical |
| AUC | area under the curve |
| BMI | body mass index |
| BQL | below quantification limit |
| CI | confidence interval |
| CM | concomitant medication |
| COVID-19 | coronavirus disease 2019 |
| CV | coefficient of variation |
| DAIDS | Division of AIDS |
| DMC | Data Monitoring Committee |
| ECG | electrocardiogram |
| eCRF | electronic case report form |
| EOFU | end of follow-up |
| EOS | end-of-study |
| EOT | end-of-treatment |
| GM | geometric mean |
| [REDACTED] | |
| ICF | informed consent form |
| ICH | International Council for Harmonisation of Technical Requirements for Pharmaceuticals for Human Use |
| ICU | intensive care unit |
| ITT-c | intent-to-treat |
| IWRS | Interactive Web Response System |
| LLN | lower limit of normal |
| LLOQ | lower limit of quantitation |
| LTFU | long-term follow-up |
| MedDRA | Medical Dictionary for Regulatory Authorities |
| NP | nasopharyngeal |
| PCR | polymerase chain reaction |
| PE | physical examination |
| PGI-C | Patient Global Impression of Change |
| PGI-S | Patient Global Impression of Severity |
| PK | pharmacokinetic(s) |
| PKI | pharmacokinetic intensive |
| PP | per protocol |
| PRO | patient-reported outcome |
| QD | once daily |
| RNA | ribonucleic acid |
| RT-PCR | reverse transcription polymerase chain reaction |
| SAE | serious adverse event |
| SAF | safety (for the analysis population) |
| SAP | statistical analysis plan |

| | |
|------------|-------------------------------------------------|
| SARS-CoV-2 | severe acute respiratory syndrome coronavirus 2 |
| SAS | Statistical Analysis Software |
| SCR | Screening |
| SoA | Schedule of Assessments |
| SUSAR | suspected unexpected serious adverse reaction |
| TEAE | treatment-emergent adverse event |
| TND | target not detected |
| WHO | World Health Organization |

1. Introduction

With millions of confirmed cases and deaths worldwide, COVID-19 continues to represent a significant medical and social burden to the world community. Despite the availability of COVID-19 vaccines, direct acting antiviral agents and monoclonal antibodies for the treatment of COVID-19, there is still a need for highly effective antiviral therapies.

EDP 235 is a highly potent inhibitor of SARS-CoV-2 3CL protease (3CLpro), one of two cysteine proteases that are indispensable for SARS-CoV-2 replication. EDP 235 is a slow-onset, -slow reversible inhibitor of 3CLpro, with an IC₅₀ (half-maximal inhibitory concentration) of 5.8 ± 3.7 nM. [REDACTED]

[REDACTED]
[REDACTED]
[REDACTED] Additional information about EDP 235 is available in the Investigator's Brochure.

This statistical analysis plan (SAP) is based upon Section 11 (Statistical Considerations) of the protocol [REDACTED] for this Phase 2 clinical study, and is prepared in compliance with International Conference on Harmonization (ICH) E9. Furthermore, this SAP contains definitions for analysis sets, derived variables, and statistical methods and data presentations for the analysis of efficacy and safety endpoints.

1.1. Objectives

1.1.1. Primary Objectives

- To evaluate the safety and tolerability of EDP 235

1.1.2. Secondary Objectives

- To evaluate the effect of EDP 235 on COVID-19 clinical symptoms and outcomes
- To evaluate the effect of EDP 235 on SARS-CoV-2 viral load
- To evaluate the pharmacokinetics of EDP 235

[REDACTED]
[REDACTED]
[REDACTED]
[REDACTED]
[REDACTED]

2. Investigational Plan

2.1. Overall Study Design and Plan

This is a randomized, double-blind, placebo-controlled, parallel group, multi-site study in non-hospitalized adult subjects who test positive for SARS-CoV-2 and have COVID-19 symptom onset within 5 days of randomization and who are not at high risk for progression to severe COVID-19. Subjects can be vaccinated or unvaccinated for COVID-19. Subjects with prior COVID-19 infection <90 days before enrollment and/or who received a COVID-19 vaccine dose <90 days before enrollment are excluded from trial participation.

[figure not shown]
Subjects will be randomized in a 1:1:1 ratio to receive either EDP 235 [REDACTED], EDP 235 [REDACTED], or placebo orally once daily for 5 days. Randomization will be stratified by age (≤ 50 years or 51 to 64 years) and by the duration of COVID-19 symptoms (≤ 3 days or >3 days and ≤ 5 days).

The study includes 4 periods:

- Screening period will occur from Day -1 to Day 1. Screening should be completed as soon as possible, and the subject will be randomized within 24 hours of signing the ICF. A subject will be considered enrolled at the time of randomization.
- Treatment period will begin with the first dose of study treatment on Day 1 and will conclude with the end-of-treatment (EOT) visit on Day 5.
- Follow-up period will begin following the last dose of study treatment and will conclude at the end of follow-up (EOFU) visit on Day 33 (28 days after the last dose of study treatment).
- Long-term follow-up period (LTFU) will begin at Day 34 and concludes at the end-of-study (EOS) visit at Week 24.

An overview of the study design is shown in **Figure 1**. Study site visits and assessments are detailed in the Schedule of Study Procedures ([Appendix 14.1](#)).

Figure 1: Study Design

2.2. Study Endpoints

The study's primary, secondary, and exploratory objectives and their associated endpoints are displayed in **Table 1**.

Table 1: Study Objectives and Endpoints

| Objectives | Endpoints |
|-------------------------------------------------------------------------------------------------------------------------------------------------------------------|--------------------------------------------------------------------------------------------------------------------------------------------------------------------------------------------------------------------------------------------------------------------------------------------------------------------------------------------------------------------------------------------------------------------------------------------------------------------------------------------------------------------------------------------------------------------------------------------------------------------------------------------------------------------------------------------------------------------------------------------------------------------------------------------------------------------------------------------------------------------------------------------------------------------------------------------------------------------------------------------------------------------------------------------------------------------------------------------------------------------------------------------------------------------------------------------------------------------------------------------------------------------------------------------------------------------------------------------------|
| 
Primary Objective
 
 To evaluate the safety and tolerability of EDP 235 | 
Primary Endpoint
 
 Safety and tolerability of EDP 235 compared to placebo as assessed by, but not limited to, adverse events (AEs), clinical laboratory results, and vital signs through Day 33 |
| 
Secondary Objectives
 
 To evaluate the effect of EDP 235 on COVID-19 clinical symptoms and outcomes | 
Secondary Endpoints
 
 Time to improvement of targeted COVID-19 signs/symptoms using the COVID-19 Symptom Diary through Day 33 Proportion of subjects with targeted COVID-19 signs/symptom improvement using the COVID-19 Symptom Diary through Day 33 Change from baseline in targeted COVID-19 signs/symptom score using the COVID-19 Symptom Diary through Day 33 Proportion of subjects with medically attended visits for COVID-19 through Day 33 Proportion of subjects requiring hospitalization (defined as ≥ 24 hours of acute care) for COVID-19 through Day 33 Proportion of subjects who require hospitalization and mechanical ventilation (invasive and non-invasive) through Day 33 Proportion of subjects with any of the following COVID-19 related events or all-cause mortality through Day 33 
 complications based on the investigator’s assessment medically attended visits hospitalizations intensive care unit (ICU) admissions requirement for supplemental oxygen or increased in supplemental oxygen requirement requirement for mechanical ventilation (invasive and non-invasive) |
| 
 To evaluate the effect of EDP 235 on SARS-CoV-2 viral load | 
 Change from baseline in SARS-CoV-2 RNA viral load through Day 33 Change from baseline in infectious SARS-CoV-2 viral load through Day 33 AUC of SARS-CoV-2 RNA viral load through Day 33 Proportion of subjects with SARS-CoV-2 RNA viral load target not detected (TND) over time through Day 33 Time to SARS-CoV-2 RNA TND through Day 33 |
| 
 To evaluate the pharmacokinetics of EDP 235 | 
 Plasma concentrations of EDP 235 |
| [REDACTED] | [REDACTED] |

concentration) of 5.8 ± 3.7 nM. Oral EDP 235 treatment in repeat dose, general nonclinical toxicity studies at up to 14 days of once-daily dosing across species was well-tolerated.

The EDP 235 doses selected for this study are [REDACTED] once daily (QD), administered with food, orally for 5 days. These doses were selected based on all relevant available nonclinical and clinical data, including repeat-dose toxicology studies, in vitro pharmacology studies with EDP 235, and clinical safety and PK data from the first-in-human phase 1 study (EDP 235-001). The selected doses are expected to provide exposures in the anticipated therapeutic range.

Following randomization on Day 1, subjects will receive the first dose of EDP 235 or placebo orally while at the study site. After the first dose, subjects will be instructed to take or be administered the study treatment orally on each of the 5 subsequent days, at approximately the same time every day (± 1 hour). Study treatment will be administered with food. The total dose administered once daily will be either:

- EDP 235 [REDACTED] orally QD
- EDP 235 [REDACTED] orally QD
- Placebo, orally QD

2.4. Dose Adjustment/Modifications

Dose modifications are not permitted for subjects in this study.

3. General Statistical Considerations

Continuous variables will be summarized using n, mean, standard deviation, median, 25th percentile (Q1), 75th percentile (Q3), minimum, and maximum values. The precision for continuous variables will be based on the precision of the data itself. The mean, median, 25th percentile, and 75th percentile will be presented to one more significant figure than the original results; the SD will be presented to two more significant figures than the original results; the minimum and maximum will be presented to the same level of precision as the original results.

Categorical variables will be summarized using frequency counts and percentages. Percentages will be presented to 1 decimal place. If the count is 0, the percentage will not be displayed. If the count equals the denominator, the percentage will be displayed as 100.

When **count data** are presented, the percentage will be suppressed when the count is zero to draw attention to the non-zero counts. A row denoted “Missing” will be included in count tabulations as needed to account for dropouts and missing values. The denominator for all percentages will be the number of subjects in the treatment group within the analysis set of interest, unless otherwise specified.

Baseline, unless otherwise specified, will be defined as the last non-missing measurement collected prior to dosing on the same date as the first dose of study treatment; if it is not available, the first measurement up to 2 hours post first dose of study treatment will be used. For

subjects who are randomized, but not treated, the baseline will be defined as the last non-missing measurement on or before the date of randomization. For height, weight and body mass index baseline will be defined as the last non-missing measurement collected on or before the date of the first dose of study treatment (without consideration of time). .

Study Day 1 is the calendar day that the first dose of the study treatment is administered. Subsequent study days are calculated as the date of assessment/event – date of the first dose + 1. If a subject is not treated, the date of randomization is used to define study day rather than the date of first dose. For assessments or events that occur before the first dose date, study day is calculated as the date of interest minus the first dose date.

Unscheduled visits measurements will be included in the analysis as follows:

- Derivation of baseline and worst post-baseline measurements.
- Individual subject data listings as appropriate.

Unscheduled visits will not be included in the by-visit summary or analyses.

No additional analysis visit windowing will be done other than what is specified for Baseline and worst post-baseline above.

When there are multiple values within an analysis visit for laboratory assessments,, the worst value (and the latest value if applicable) will be used in the analysis. For graded labs, worst is defined as the highest grade and if there is more than one record of the same grade for a given analysis visit, the latest value will be selected for analysis. For non-graded labs, worst is defined as the smallest value for criteria below a certain threshold or the largest value for criteria above a certain threshold. If a subject has a value below the threshold and above the threshold, the value furthest from the threshold will be chosen.

For all other assessments, if there are multiple values within an analysis visit the latest record will be selected for analysis.

All diary data will be summarized based on the actual day.

Time-to-event variables are defined from the date of first dose.

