3.1. Incomplete and Missing Data

Imputation rules for missing dates of prior/concomitant medications, including COVID-19 vaccinations and prohibited medications, and procedures are provided in [Appendix 14.5](#).

Imputation rules for missing AE data are provided in [Appendix 14.5](#).

Data that are continuous in nature but are reported in the form $<x$, $>x$, $\leq x$, or $\geq x$ (where x is considered as the limit of quantitation) will be set to limit of quantitation value with the following exceptions:

- Efficacy endpoint data will be imputed as detailed in [Appendix 14.5](#).
- PK concentrations data will be imputed as detailed in [Appendix 14.5](#).

- Other incomplete/missing data will not be imputed, unless specified otherwise.

All analyses will be conducted using SAS Version 9.4 or higher. Unless otherwise stated, a two-sided test will be used at a significance level (alpha) of 0.05 for all analyses. Two-sided 95% confidence intervals (CI) will be provided when appropriate.

Summary Tables and Figures will be presented by treatment group and will be labelled as follows:

- “EDP 235 [REDACTED]”
- “EDP 235 [REDACTED]”
- “Placebo”

All subject data will be presented in individual subject data listings. Dates will be shown in subject listings as they have been recorded. Unless otherwise stated, unscheduled visit results will be included in date/time chronological order, within subject listings only. All listings will be sorted by subject number, date/time and visit. The treatment group (randomized) as well as subject’s sex and age will be stated on each listing. Unless otherwise stated, data listings will be based on all subjects randomized.

When no data are available for a table or listing, an empty page with the title will be produced with suitable text (e.g., “There are no records for this table/listing.”). For analyses where convergence or the analysis cannot be performed, “NC” (not calculable) will be presented in summary tables.

For the reporting of this study both CDISC SDTM (SDTM Implementation Guide version 3.3 or later) and ADaM (ADaM Implementation Guide version 1.3 or later) standards will be applied.

[REDACTED]

[REDACTED]

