7.2. Clinical Laboratory Evaluations

Central laboratory values will be used for analysis and results will be graded using the National Institute of Allergy and Infectious Diseases Division of AIDS (DAIDS) Table for Grading the Severity of Adult and Pediatric Adverse Events Corrected Version 2.1 dated July 2017.

Laboratory values and change from baseline will be summarized overall and by treatment group for scheduled visits. Shift tables by scheduled visit and worst post-baseline will also be generated by reference range and grade as follows :

Additionally, results will be summarized according to any value greater than the high limit, 2x upper limit of normal (ULN) or 3x ULN and any value less than the lower limit, 2x lower limit of normal (LLN) or 3x LLN (i.e 1/2 of LLN or 1/3 of LLN).

All laboratory data will be included in the data listings. Test values greater than the high limit, 2x ULN, 3x ULN, less than the lower limit, 2x LLN and 3x LLN.

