7.3. Vital Sign Measurements

Vital sign observed, change from baseline and pulse oximetry measurements will be summarized by treatment by visits.

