7.4. Electrocardiogram

All Electrocardiogram (ECG) results will be summarized by treatment group and visit in the Safety population and a listing will be presented of all results with abnormalities flagged.

8. Efficacy Analysis

Unless otherwise specified, efficacy analyses will be performed using ITT-c population and the following methods will be implemented:

For time to event endpoints time and date will be used and 24 hours will be considered as a day. Descriptive statistics using the Kaplan-Meier method will include the median, 25th percentile, and 95% CIs (log-negative-log transformation). Additionally, the cumulative event rate (SE) will be summarized by treatment group and presented graphically over time. For between group comparisons, Cox Proportional Hazards models (tie handling will be addressed first using the exact method then with Efron's method if the exact method does not converge) will include treatment group, randomization stratification factors of age (≤ 50 years or 51 to 64 years) and duration of COVID-19 symptoms (≤ 3 days or >3 days and ≤ 5 days), and the baseline value of the endpoint. The hazard ratios with associated 95% CIs (Wald) and p-values (analysis of maximum likelihood estimates) comparing EDP 235 [REDACTED] versus Placebo, and EDP 235 [REDACTED] versus Placebo will be reported. Model assumptions will be checked via a log-negative-log plot and/or Schoenfeld residuals as appropriate. Subjects who do not achieve the specified endpoint will be censored with time imputed as treatment start time as follows:

COVID-19 diary:

- Subjects who have not been followed through the Day 33 visit (discontinuation from study or incomplete follow-up at the time of analysis) or completed Day 33 diary will be censored at Day 33.

Other time to event endpoints:

- Subjects who discontinued from the study will be censored at Day 33.
- Subjects who have completed the Day 33 visit will be censored at Day 33 Visit Date.

For treatment comparisons of change from baseline endpoints, analysis of covariance (ANCOVA) models will include treatment group, randomization stratification factors of age (≤ 50 years or 51 to 64 years) and duration of COVID-19 symptoms (≤ 3 days or >3 days and ≤ 5 days) and baseline value of the endpoint as the covariate. The least-squares means, SE, and 95% CIs will be presented for individual groups and the difference between groups. The p-value for

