^a During the Follow-up period (Day 6 through Day 33), if the participant has symptom recurrence or symptom worsening, an unscheduled visit should be done within 2 days of patient reported symptom recurrence or worsening. At the unscheduled visit, NP swabs will be collected in addition to clinical assessments deemed necessary by the Investigator.

^b Screening assessments should occur within 24 hours of randomization.

- c. D1 assessments are to be done only in randomized participants. Randomization, predose baseline measurements, and dosing must occur on the same calendar date.
- d. These assessments should be done predose as baseline measurements
- e. Participants who discontinue treatment before completing 5 days of dosing should return to the study site within 24 hours of their last dose to complete EOT procedures and proceed to complete all follow up assessments 4, 9 and 28 days (EOFU visit) after their last dose of study drug. Participants who discontinue the study before Day 33 (EOFU) should return to the study site within 24 hours and no more than 48 hours later to complete the EOFU procedures.
- f. Visits may be completed at the study site or by study site personnel via a home visit, if feasible.
- g. These assessments are only required for participants who discontinued the study before Day 5 (ie, do not have an EOT visit before discontinuing the study) or participants who discontinued the study after Day 5 and before Day 14. These participants should have an EOFU visit with additional assessments as indicated
- h. For the Week 12 and Week 24 assessments, paper questionnaires may be used for the Global Impression Questions and EQ-5D-5L and transcribed into the eCRF.
- i. At Week 12 and Week 24, study staff will contact each participant to ask if they have COVID-19 signs and symptoms and record that information into the AE eCRF.

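### Vital-sign, pulse-oximetry and ECG values from unscheduled visits, including visits for worsening symptoms, enter no vital-sign or ECG summary by arm, although the SAP already has the derivation that would include them

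*SAP*

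**What the plan says.** SAP Section 3 (General Statistical Considerations) sets the rule for unscheduled visits. They are used for "Derivation of baseline and worst post-baseline measurements" and for subject listings, and then: "Unscheduled visits will not be included in the by-visit summary or analyses". Section 3.1 gives the same default: "Unless otherwise stated, unscheduled visit results will be included in date/time chronological order, within subject listings only".

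The safety sections apply this rule differently:

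- Section 7.2, laboratory: "Shift tables by scheduled visit and worst post-baseline will also be generated by reference range and grade". It also plans summaries of values beyond multiples of the normal limits.
- Section 7.3: "Vital sign observed, change from baseline and pulse oximetry measurements will be summarized by treatment by visits". Nothing else is planned.
- Section 7.4: "All Electrocardiogram (ECG) results will be summarized by treatment group and visit in the Safety population". It adds a listing in which abnormal results are flagged.

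Footnote a of the Schedule of Study Procedures (Appendix 14.1) concerns subjects whose symptoms recur or worsen between Day 6 and Day 33: "an unscheduled visit should be done within 2 days of patient reported symptom recurrence or worsening". At that visit "NP swabs will be collected in addition to clinical assessments deemed necessary by the Investigator".

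Table 1 in Section 2.2 names vital signs, with adverse events and laboratory results, in the primary endpoint through Day 33, compared with placebo. The schedule counts pulse oximetry among the vital signs.

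**The concern.** Leaving unscheduled visits out of by-visit tables is ordinary practice, because such visits have no nominal time point. The usual counterpart is a worst post-baseline table that takes them in. Section 3 provides for that derivation in general terms, but 7.3 and 7.4 never use it.

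The omission is not random with respect to outcome. Footnote a makes deterioration itself the reason for a visit, so among the values left out of the summaries are those most likely to be abnormal. If one arm had more subjects with low saturation or an abnormal heart rate at such visits, the vital-sign tables would not show it. A reader would have to count cases from listings, which give no comparison between arms. For vital signs this touches a named component of the primary endpoint. ECG is not named there, so for ECG the point rests on ordinary completeness of safety reporting.

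**Working it through.** No arithmetic figure in the plan is at issue. The check follows one post-baseline value, recorded at an unscheduled visit, through each planned output.

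| Data type | By-visit summary | Worst post-baseline summary by arm | Listing | Where the unscheduled value ends up |
|---|---|---|---|---|
| Laboratory (7.2) | Yes, unscheduled values excluded | Yes, shift tables | Yes | Summary table and listing |
| Vital signs and pulse oximetry (7.3) | Yes, unscheduled values excluded | None planned | Yes, under the general rule in 3.1 | Listing only |
| ECG (7.4) | Yes, unscheduled values excluded | None planned | Yes, abnormalities flagged | Listing only |

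1. **Does Section 3 forbid a worst post-baseline table for vital signs or ECG?** No. The allowance is not limited to laboratory data. The gap is that 7.3 and 7.4 ask for no output that would use it.

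2. **Does the reference in 7.4 to all ECG results bring unscheduled ones in?** Not on a plain reading. The summary is by visit, and Section 3 keeps unscheduled visits out of by-visit summaries.

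3. **How long does the trigger in footnote a run?** From Day 6 to Day 33, which is 33 − 6 + 1 = 28 of the 33 study days that the endpoint covers. It begins after the five-day treatment period.

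4. **What is scheduled in that time?** After Day 5 the vital-signs row carries two ordinary marks and the ECG row one. Each row also has one mark qualified by footnote g. The columns are misaligned in the text available here; the ordinary marks most plausibly belong to Days 9 and 14 for vital signs. Footnote g requires the qualified assessment only of subjects who left the study before Day 5, or after Day 5 and before Day 14. Required measurements are therefore sparse late in follow-up, and unscheduled visits matter more there.

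5. **What happens to repeat values at one visit?** Section 3 takes the worst laboratory value but the latest record for other assessments. An abnormal vital sign followed by a normal recheck at the same scheduled visit is thus represented by the recheck. A worst post-baseline summary built from all records would cover this case too.

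6. **Can the number of affected measurements be estimated?** No. Footnote a requires only swabs; other assessments are at the investigator's discretion, and the SAP gives no expected number of such visits.

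**The case against.** The strongest opposing case is that the rule is normal, no statement in the SAP is false, and clinically important deterioration is tabulated elsewhere. Much of this stands:

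- An abnormality reported as an adverse event enters the TEAE tables, and the SAE tables if serious (Section 7.1).
- Oxygen supplementation is among the concomitant therapies summarised by treatment group (Section 6.3).
- Medically attended visits, hospitalisation, ICU admission, oxygen requirement, ventilation and death are compared between arms (Sections 8.2.3 to 8.2.6).
- Continuous summaries include quartiles, minimum and maximum (Section 3), so an extreme value selected at a scheduled visit is visible in its arm and visit.
- The DMC reviews safety data during the study (Section 11).

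These routes do not fully replace the missing table. Adverse-event reporting depends on the investigator's judgement, and the SAP does not regard it as sufficient for laboratory values. The Section 8 summaries use the ITT-c population by default, a subset of the Safety population. A minimum or maximum does not say how many subjects were abnormal. DMC review does not supply a table for the final report.

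Two stronger readings are tempting, and the SAP does not support them. A reader might infer that values taken at worsening visits reach no safety table of any kind; the routes above show that the clinical event often will, even though the measured value will not. A reader might also infer that every vital-sign and ECG value after Day 14 is lost to the summaries. Footnote g says when a Day 33 assessment is required, not that others may not have one, and a Day 33 value recorded in a completer belongs to a scheduled visit.

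It is also fair that symptom-driven assessment makes the number of measurements differ between subjects, and possibly between arms. That calls for a caution on the table, not for leaving it out.

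**Conclusion.** The point holds as a gap between sections that should be closed before unblinding. Followed as written, the plan gives unscheduled laboratory values a place in a summary by arm but confines unscheduled post-baseline vital-sign, pulse-oximetry and ECG values to listings, including those prompted by worsening.

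Its size cannot be stated as a number or a share, because neither the count of unscheduled visits nor the measurements taken at them is given. It could be small. The importance comes from the selective nature of the omission and from vital signs through Day 33 being part of the primary safety endpoint; for ECG the second reason does not apply. Tabulation of recognised clinical events and of scheduled-visit extremes limits the damage.

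The conclusion assumes that 7.3 and 7.4 list all the planned vital-sign and ECG summaries, and that some investigators will measure vital signs or record an ECG at the visits under footnote a.

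**What to change.** Add to Sections 7.3 and 7.4 a per-subject worst post-baseline summary by treatment group in the Safety population. State that it draws on all post-baseline records, including unscheduled visits and repeats within a visit:

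- minimum oxygen saturation;
- minimum and maximum heart rate, systolic and diastolic blood pressure;
- maximum temperature and respiratory rate;
- maximum ECG intervals.

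Report descriptive statistics and the number and percentage of subjects per category, with the sponsor fixing the categories in the SAP before unblinding. Footnote each table to say that unscheduled assessments are driven by symptoms, so the number of assessments varies by subject; showing that number by arm would help interpretation. Keep the by-visit tables and the Section 3 exclusion as planned.

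The cost is a few tables from data already collected, using a derivation that Section 3 already permits. No change to visits or procedures is needed.
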